3.3. Dose Escalation

3.3.1. Dose Escalation: Monotherapy Cohort A1

The study will be conducted as a limited 3+3 phase 1 dose escalation study with potential expansion cohorts. Clinical safety data in healthy volunteers suggest very few toxicities at 100 to 200 mg BID for up to 14 days. A conservative starting dose of 100 mg BID has been chosen and will be escalated according to Table 2 below:

Dose Level	Dose
0	100 mg BID
1	200 mg BID
2	250 mg BID
3	300 mg BID
4+	TBD* mg BID

Table 2: Monotherapy Dose Levels

*To be determined

A conventional "3+3" patient enrollment scheme will be followed during the dose escalation part of the study. Patients will be dosed with MS-553 by mouth twice daily at an initial dose (dose level 0, DL 0) of 100 mg BID daily in 28-day cycles. MS-553 shall be taken with food.

At least 3 patients will be enrolled at starting dose level 0 (100 mg BID).

After completion of dose level 3 (DL 3), the dose escalation of MS-553 can continue in 50 mg BID increments (or lower if an intermediate dose level is introduced) until a MTD is reached. Or the Safety Review Committee and/or the Sponsor may declare an initial RP2D, if further dose escalation is not warranted prior to reaching MTD. Furthermore, in order to facilitate initial RP2D determination, select cohort(s) may be expanded up to 10 patients total in a cohort to assess the safety and clinical activity of MS-553 provided that the dose does not exceed the MTD and the Safety Review Committee, upon reviewing the safety and tolerability, efficacy, and available PK and PD data, agrees. The DLT period is defined in this cohort as 28 days.

3.3.2. Dose Escalation: General Principles

During the first cycle of any dose level, if ≤ 1 Dose Limiting Toxicity (DLT; as defined in Section 3.3.1) is observed, then escalation to the next higher dose level will follow the 3+3 design and proceed when 3/3 or 5/6 patients have completed one 28-day treatment cycle without a DLT. If at least 1 of 3 patients experiences a DLT at any dose level, the cohort will be expanded to 6 patients. If $\geq 2/3$ or $\geq 2/6$ patients experience a DLT within a cohort, the MTD will be considered to have been exceeded. No additional patients will be enrolled in that cohort, and dose escalation will stop. If at least 3/3 or 5/6 patients have completed one 28-day treatment cycle at the previous dose level without a DLT, then that dose may be accepted as the MTD. At Sponsor discretion, additional patients may be enrolled into a cohort where ≤ 1 patient develops a DLT to obtain additional safety, PK, PD, and/or efficacy data.

If greater than 1/6 patients experience a DLT at DL 1, then 100 mg BID may be declared the MTD, or intermediate dose levels and/or alternative dosing schedules may be evaluated upon review of safety, pharmacodynamic, and/or pharmacokinetic data.

Each dose cohort will include a minimum of 3 evaluable patients for assessment of DLT. In order to be considered evaluable for DLT, patients must meet at least one of the following criteria:

- 1. Complete dosing through the DLT period and receive at least 75% of MS-553 intended doses during that time.
- 2. Discontinue due to DLT

During the DLT evaluation period, non-evaluable patients who discontinue treatment before DLT period is complete for reasons other than study drug-related toxicities (e.g., progressive disease, non-compliance) or do not receive at least 75% of MS-553 intended doses in the DLT period, will be replaced with additional patients enrolled at the same dose level. After a DLT is resolved or reversed to \leq Grade 1, the study drug may continue at a lower dose level at the discretion of the investigator.

A decision on dose escalation to the next dose level will be based on evaluation of the clinical safety profile, and may also include evaluation of MS-553 exposure in treated patients. After the completion of each cohort, safety and PK data (if available) will be reviewed and a decision on dose escalation will be determined by the Investigators, the Safety Review Committee, and the Sponsor.

During the dose escalation period, intra-patient dose escalation will be permitted at the discretion of the study investigators and after discussion with the medical monitor and Sponsor, if the following criteria are met:

- The next higher dose for the regimen has been demonstrated to be safe by at least 3 patients and all 3 patients complete one cycle without experiencing any DLT.
- 2. The patient who will receive the higher dose has not experienced a DLT and has also completed at least 2 cycles of therapy at their current dose.
- 3. Intra-patient dose escalation can be increased only by one dose level at a time.

After completion of each dose escalation cohort, the SRC will review clinical safety and tolerability data as well as PK data available at the time for all patients in order to confirm dose escalation to the next dose level. Based on the SRC's review, a cohort may be expanded, or an intermediate or a lower-than-planned dose level or an alternative dosing schedule may be evaluated.

All patients will continue to be monitored for approximately 30 days (+7 days) after treatment discontinuation for development of any late treatment emergent adverse events. Any such late adverse events will be considered in the determination of the MTD/initial RP2D and dose schedule to be taken forward into the expansion phase of the study.

While the

MTD was not reached, an initial RP2D was identified. **Second Second** the SRC reviewed all available efficacy, safety, PK and PD data of Cohort A1 and some Cohort A2 patients and agreed on an updated RP2D with a ramp-up dosage regimen as shown in Table 3 below.

MS-553	Oral Daily Dose
Weeks 1 to 4 (Cycle 1)	150 mg BID
Weeks 5-8 (Cycle 2)	200 mg BID
Weeks 9 and beyond	250 mg BID
(Cycle 3+)	

Table 3:Initial Recommended Phase 2 Dose

The two new dose schedules are designated as dose schedule 1 (DS1) and dose schedule 2 (DS2) are as follows:

Dose Schedule 1 (DS1)

	MS-553 Oral Daily Dose
Week 1	150 mg BID
Week 2	200 mg BID
Week 3 and beyond	250 mg BID

Dose Schedule 2 (DS2)

	MS-553 Oral Daily Dose
Cycle 1 and beyond	225 mg BID

Twenty of the 40 additional patients will be treated with DS1 and the other 20 patients with DS2. The patients will be allocated to either DS1 or DS2 in alternating fashion, according to the sequence of their enrollment. For example, the first enrolled patient will be allocated to DS1, the second patient to DS2, the third patient to DS1, the fourth to DS2, and so on.

The optional expansion cohort (Cohort A3) will be closed to accommodate the new dose testing plan.

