Patients who discontinue treatment for progressive disease and/or use of other CLL/SLL therapy will be followed for survival every 24 weeks (± 7 days) for up to 3 years. Patients who discontinue treatment for reasons other than progressive disease, use of other CLL/SLL therapy, death, or withdrawal of consent will have response assessments every 12 weeks (± 7 days) until progressive disease occurs. Thereafter they will be followed for survival every 24 weeks (± 7 days) for up to 3 years. All patients will discontinue survival follow-up upon completion of 3 years of survival follow-up, withdrawal of consent, death, or study closure, whichever is the earliest.

Dose limiting toxicity, Dose Adjustments and Management of DLTs

Cohort A1

At least 3 patients will be enrolled at starting dose level 0 (100 mg BID for Cohort A1, MTD/initial RP2D level -1 for Cohort B1). During the first cycle of any dose level, if \leq 1 DLT is observed, then escalation to the next higher dose level will follow the 3+3 design and proceed when 3/3 or 5/6 patients have completed one 28-day treatment cycle without a DLT. If at least 1 of 3 patients experiences a DLT at any dose level, the cohort will be expanded to 6 patients. If \geq 2/3 or \geq 2/6 patients experience a DLT within a cohort, the MTD will be considered to have been exceeded. No additional patients will be enrolled in that cohort, and dose escalation will stop. If at least 3/3 or 5/6 patients have completed one 28-

day treatment cycle at the previous dose level without a DLT, then that dose may be accepted as the MTD. At Sponsor discretion, additional patients may be enrolled into a cohort where \leq 1 patient develops a DLT to obtain additional safety, PK, PD, and/or efficacy data.

If greater than 1/6 patients experience a DLT at DL 1, then 100 mg BID may be declared the MTD, or intermediate dose levels and/or alternative dosing schedules may be evaluated upon review of safety, pharmacodynamic, and/or pharmacokinetic data.

Cohort B1

In Cohort B1, at least 3 patients will be enrolled at starting dose level of 150 mg BID. The general principles of dose escalation and DLT evaluation rules described in Cohort A1 are applicable to Cohort B1.

Cohort C1

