In Cohort C1, at least 3 patients will be enrolled at starting dose level of 150 mg BID. The dosing rules for Cohorts A1 and B1 will be similarly applied to Cohort C1. For the dose levels of MS-553 up to and including 225 mg BID, the DLT evaluation period will be through Cycle 4 (16 weeks). During the DLT evaluation period, if \leq 1 DLT is observed, then escalation to the next higher dose level will follow the 3+3 design and proceed when 3/3 or 5/6 patients have completed four treatment cycles without a DLT. If at least 1 of 3 patients experiences a DLT at any dose level, the cohort will be expanded to 6 patients. If \geq 2/3 or \geq 2/6 patients experience a DLT within a cohort, the MTD will be considered to have been exceeded. At Sponsor discretion, additional patients may be enrolled into a cohort where \leq 1 patient develops a DLT to obtain additional safety, PK, PD, and/or efficacy data.

Determination of DLT for dosing Cohorts A1

Each dose cohort will include a minimum of 3 evaluable patients for assessment of DLT. In order to be considered evaluable for DLT, patients must meet at least one of the following criteria:

- 1. Complete one 28-day cycle and receive at least 75% of MS-553 intended doses in Cycle 1
- 2. Discontinue due to DLT

During the DLT evaluation period for each cohort, non-evaluable patients who discontinue treatment before one cycle is complete for reasons other than study drug-related toxicities (e.g., progressive disease, non-compliance), or do not receive at least 75% of MS-553 doses, will be replaced with additional patients enrolled at the same dose level. After a DLT is resolved or reversed to \leq Grade 1, the study drug may continue at a lower dose level at the discretion of the investigator.

A decision on dose escalation to the next dose level will be based on evaluation of the clinical safety profile and may also include evaluation of MS-553 exposure in treated patients. After the completion of each cohort, safety and PK data (if available) will be

reviewed and a decision on dose escalation will be determined by the Investigators, the Safety Review Committee, and the Sponsor.

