3.3.3. Dose Escalation: Combination Cohort B1

Once the MTD or initial RP2D is established for the monotherapy Cohort A1, enrollment in Cohort B1 will begin at 150 mg BID. The principles outlined in Section 3.3.2 will be followed for the Dose Escalation for the combination regimens. One or more 3+3 dose escalation cycles may be undertaken to determine an initial RP2D for MS-553 for each combination expansion cohorts. At least two dose levels are planned for Cohort B1. The dosing schedule and DLT evaluation periods are described in the table below.

Table 4. Dosing Schedule and DET Evaluation Tenous for Conort DI				
MS-553 Dose Levels	Dosing Schedule	DLT Evaluation Period		
150 mg BID	In 28-day cycles	Cycle 1		
200 mg BID	In 28-day cycles	Cycle 1		

Table 4: Dosing Schedule and DLT Evaluation Periods for Cohort B1

MTD determination, DLT and safety assessments will follow the general principles outlined in Cohort A1. Initial RP2D of MS-553 in the combination therapy is expected to be reached before the dose escalation reaches 250 mg BID, the high dose level of MS-553 monotherapy under testing. Intermediate dose levels (i.e. at 25 mg increment) or lower dose levels may also be evaluated as determined by the Investigators, the SRC and Sponsor until the MTD or initial RP2D for the combination is determined.

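### With 2/3 or 3/3 DLTs the 3+3 text both expands the cohort to six and bars further patients; B1 and C1 inherit the conflict

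*Combined protocol and SAP*

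**What the plan says.** **Core rule.** Section 3.3.2 and the synopsis (DLT section, Cohort A1) give these instructions in sequence:

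- Escalate when 3/3 or 5/6 patients have completed the cycle free of DLT.
- "If at least 1 of 3 patients experiences a DLT at any dose level, the cohort will be expanded to 6 patients".
- If two or more of three, or two or more of six, have a DLT, the MTD counts as exceeded.
- "No additional patients will be enrolled in that cohort, and dose escalation will stop".
- The sponsor may add patients for further data only to a cohort with no more than one DLT.

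**Cohort B1.** The synopsis says: "The general principles of dose escalation and DLT evaluation rules described in Cohort A1 are applicable to Cohort B1". Section 3.3.3 says: "The principles outlined in Section 3.3.2 will be followed for the Dose Escalation for the combination regimens".

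**Cohort C1.** The synopsis says: "The dosing rules for Cohorts A1 and B1 will be similarly applied to Cohort C1". It then restates the rule with a four-cycle (16-week) DLT period. The expansion sentence is kept, but the text runs straight from the MTD statement to the discretionary option: "patients experience a DLT within a cohort, the MTD will be considered to have been exceeded. At Sponsor discretion". The sentence barring further enrolment is not there. Section 3.3.4 refers back to the A1 principles.

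**Two related places.**

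- Section 3.4.1 describes the MTD as the highest level at which fewer than 2/6 patients finished Cycle 1 free of DLT.
- In the synopsis, a parenthesis in the A1 paragraph gives the B1 start as level -1 relative to the MTD or initial RP2D. The synopsis B1 text and Sections 3.1.2 and 3.3.3 give 150 mg BID.

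**The concern.** A dose-escalation rule should lead from each observed DLT count to one action. Here, two of the four possible results in the first three patients lead to opposite actions. A site or sponsor following the expansion sentence would enrol three more patients at a dose that the same paragraph already places above the MTD.

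The C1 paragraph is the weakest point. Read alone, it expressly says to expand, and the bar has to be inferred from cross-references and from the limit on discretionary enrolment. C1 also has the longer DLT window.

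The DLT rate in these periods is part of the primary safety endpoint (Section 2.4), so its denominator would also depend on which sentence was followed.

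**Working it through.** **1. Each result against the two sentences.**

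| DLTs in first 3 | Expansion sentence applies | MTD-exceeded and no-enrolment sentences apply | DLTs of 6 if expanded |
|---|---|---|---|
| 0 | no | no | not expanded |
| 1 | yes | no | 1 to 4 |
| 2 | yes | yes | 2 to 5 |
| 3 | yes | yes | 3 to 6 |

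Both sentences apply at 2/3 and 3/3. If expanded, both always end at 2/6 or more, so the MTD conclusion cannot change.

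**2. The plan's own figure.** The synopsis gives 3 to approximately 12 patients for B1 and for C1, with at least two dose levels. Two full levels give 2 x 6 = 12, which matches the top of the range. Enumerating all paths over two levels under the DLT rules alone:

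- If 2/3 or 3/3 stops enrolment, the totals are 3, 6, 9 or 12.
- If 2/3 or 3/3 expands, the totals are 6, 9 or 12.

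The stated minimum of 3 fits the first reading. It does not settle the matter: a total of 3 could also follow from declaring an initial RP2D, and Section 3.1.3 gives the C1 range per dose group.

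**3. How often, and how many patients.** The documents give no DLT rate, so the true rate p is **assumed** to be 0.10, 0.20 or 0.33. Let X be the number of DLTs in the first three, X ~ Binomial(3, p).

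- Conflict arises: P(X >= 2) = 3p²(1-p) + p³. At p = 0.33 this is 3 x 0.1089 x 0.67 + 0.0359 = 0.255.
- Escalation, both readings: (1-p)³ + 3p(1-p)² x (1-p)³. Expanding after 2/3 or 3/3 adds no path to escalation.
- Mean enrolment per level, stop reading: 3 + 3 x P(X = 1).
- Mean enrolment per level, expand reading: 3 + 3 x P(X >= 1).
- Difference: 3 x P(X >= 2).

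| Assumed p | P(X >= 2) | P(escalate), both readings | Mean n, stop | Mean n, expand | Difference |
|---|---|---|---|---|---|
| 0.10 | 0.028 | 0.906 | 3.73 | 3.81 | 0.08 |
| 0.20 | 0.104 | 0.709 | 4.15 | 4.46 | 0.31 |
| 0.33 | 0.255 | 0.434 | 4.33 | 5.10 | 0.76 |

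At each p the difference is a maximum, reached only if the expansion sentence always prevails. It grows with p: at p = 0.50 it is 3 x 0.500 = 1.50 patients.

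**4. Exposure per expansion.** Three patients add up to 3 x 28 = 84 patient-days of DLT window in B1 and 3 x 4 x 28 = 336 in C1. At p = 0.33, the chance of at least one DLT among the three is 1 - 0.67³ = 0.70.

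**5. Reported rate.** An initial 2/3 (67%) would become 2/6 to 5/6 (33% to 83%). An initial 3/3 would become 3/6 to 6/6 (50% to 100%).

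**6. The two smaller places.**

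- Fewer than 2/6 free of DLT means at least 5/6 with a DLT. That reverses the 5/6 DLT-free condition in Section 3.3.2.
- The monotherapy levels in Table 2 are 100, 200, 250 and 300 mg BID. No step down that table gives 150 mg BID.

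**The case against.** The strongest reply is that the text, read as a whole, points one way:

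- The expansion sentence is general and the sentences after it are specific.
- A separate two-of-three trigger would be redundant if every such cohort went on to six.
- The design is called a conventional 3+3.
- Discretionary enrolment is limited to a cohort in which no more than one "patient develops a DLT to obtain additional safety, PK, PD, and/or efficacy data".
- A1 cohorts may be enlarged to ten only at doses not above the MTD.
- The stated minimum of 3 fits the stop reading.
- Section 3.3.3 applies Section 3.3.2 to the combination regimens in the plural, so the enrolment bar reaches C1 as well.
- Decisions rest with the Investigators, the Safety Review Committee and the sponsor, and no hypothesis is tested on the DLT rate.

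Most of this stands as evidence of the likely intent, and it makes the extra exposure less probable. It does not remove the conflict, because neither sentence is made subject to the other. The committee's escalation review follows completion of a cohort, and whether a cohort with 2/3 DLTs is complete is exactly what the text leaves open. The synopsis does promise ongoing safety review, but that is oversight and not a rule.

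Two further limits are fair. The documents do not say how much B1 or C1 escalation remains. The B1-start parenthesis cannot be fully resolved either, because intermediate levels are permitted and the text around the initial RP2D is incomplete in the public copy.

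**Conclusion.** The concern holds. For 2/3 and 3/3 DLTs, the operative text gives two incompatible enrolment instructions. B1 and C1 inherit them, and the C1 restatement lacks the explicit bar.

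The escalation and MTD decisions are unaffected. What is at stake is up to three more patients per affected cohort at a dose the plan already regards as too toxic, and the denominator of the DLT rate. The average size is small at low DLT rates and approaches one patient per level at 33%. These averages rest on assumed rates, independent patients and the expansion sentence always being followed.

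A1 escalation appears finished (Section 3.3.2 reports that the MTD was not reached), so the practical relevance is to B1 and C1. The Section 3.4.1 wording and the B1-start parenthesis are drafting errors with little present effect. Section 3.4.1 also allows the initial RP2D, and the other B1 passages agree with one another.

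**What to change.** Reconcile the passages so that each result (0/3, 1/3, 2/3, 3/3, at most 1/6, at least 2/6) has one stated action, and apply it expressly to A1, B1 and C1. It is enough to:

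- clarify the scope of the expansion sentence in Section 3.3.2 and in the synopsis A1 and C1 paragraphs;
- state in the C1 paragraph whether enrolment stops once the MTD is exceeded;
- align the MTD wording in Section 3.4.1 with the same rule;
- give the B1 starting level in one form throughout.

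Which rule and which starting level apply is for the sponsor to decide. The cost is wording in the next amendment, with no change to planned sample size or procedures.

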3.3.5. Dose Limiting Toxicity Definition

Dose limiting toxicities (DLT) occurring during DLT period appropriate for the cohort will be used to determine which dose of MS-553 will be examined in expansion cohorts. Toxicities will be assessed utilizing the National Cancer Institute Common Terminology Criteria for Adverse Events (NCI CTCAE v5.0) in Appendix 4.

Dose limiting toxicities (DLT) are defined as any of the following treatment-emergent events occurring from Cycle 1 Day 1 (after administration of MS-553) through the end of the DLT period (unless the event is determined to be unrelated to the drug):

- 1. Death
- 2. Hematologic toxicities:
 - Grade 4 neutropenia for \geq 7 days
 - Grade 3 febrile neutropenia: absolute neutrophil count (ANC) <1000/mm³ and single temperature >38.3°C (101°F) or a sustained temperature ≥38°C (100.4°F) for > 1 hour
 - Grade 4 thrombocytopenia \geq 14 days (patients with baseline platelet count of \geq 50 x 10⁹/L)
 - Grade 4 thrombocytopenia ≥ 28 days (patients with baseline platelet count < 50 x $10^9/L)$
 - \geq Grade 3 thrombocytopenia associated with \geq Grade 2 hemorrhage
 - New ≥ Grade 3 anemia requiring transfusion in a patient previously transfusionindependent.
- 3. Nonhematologic toxicities:
 - Any other ≥ Grade 3 toxicity not reversed to any one of the following three conditions in 7 days with appropriate intervention: a) baseline; b) ≤ Grade 1; or c) a status considered to be controlled by the Safety Review Committee (For example, isolated ≥ Grade 3 laboratory toxicity [e.g., electrolyte abnormalities] not associated with clinical signs or symptoms and is reversed to Grade 2 with appropriate intervention in 7 days is not considered a DLT.)
 - Any treatment-related adverse event (TEAE) requiring >25% of doses of scheduled study drug to be withheld during the DLT period.

All patients will continue to be monitored for approximately 30 days (+7 days) after treatment discontinuation for development of any late treatment emergent adverse events. Any such late adverse events will be considered in the determination of the MTD/initial RP2D and dose schedule to be taken forward into the expansion phase of the study.

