3.5. Safety Review Committee

The SRC will monitor the safety of all patients in the dose escalation segment. The Committee will receive all available demographics, PK, and safety data (including, but not limited to, lab and ECG results, physical exam findings, vital signs, adverse events) for all patients dosed within a given cohort in order to make a decision regarding dose escalation to the next dose level. Based on the SRC's review, a dose escalation cohort may be expanded or an intermediate or a lower-than-planned dose level may be evaluated. The SRC will include the Sponsor representatives, the medical monitor, and Principal Investigators.

A separate Safety Management Plan outlines the roles and responsibilities for those involved in the collection and processing of Serious Adverse Events (SAEs), and pregnancies for this clinical study.

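### A patient whose DLT costs more than 25% of MS-553 doses and who then resumes is classed as non-evaluable and replaced, and the plan does not say whether that DLT stays in the 3+3 count

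*Combined protocol and SAP*

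**What the plan says.** Section 3.3.2 requires that "Each dose cohort will include a minimum of 3 evaluable patients for assessment of DLT". A patient becomes evaluable by meeting at least one of two criteria: dosing through the DLT period with at least 75% of intended MS-553 doses received, or "Discontinue due to DLT". Having a DLT is not itself a criterion. Non-evaluable patients who "do not receive at least 75% of MS-553 intended doses in the DLT period, will be replaced with additional patients". The exception for drug-related toxicity in that sentence belongs to the clause on stopping treatment early, not to the 75% clause. The synopsis repeats the same structure for Cohorts A1, B1 and C1.

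Three other statements bear on the same patient:

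- Section 3.3.5 lists as a DLT a treatment-related event "requiring >25% of doses of scheduled study drug to be withheld during the DLT period".
- Section 3.3.2 says that after a DLT resolves "the study drug may continue at a lower dose level at the discretion of the investigator".
- The 3+3 rule in Section 3.3.2 stops escalation when at least 2 of 3 or 2 of 6 "patients experience a DLT within a cohort, the MTD will be considered to have been exceeded". Section 3.3.5 adds that DLTs "occurring during DLT period appropriate for the cohort will be used to determine which dose of MS-553 will be examined in expansion cohorts".

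**The concern.** The withheld-dose DLT and the 75% exposure threshold are exact complements. Any patient who meets the first must fail the second. If MS-553 then resumes, the second route to evaluability is not met either, so a patient with a protocol-defined DLT is labelled not evaluable for DLT and replaced.

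No passage says whether a replaced patient's DLT stays in the numerator, or which denominator then applies. The 3+3 count feeds the MTD or initial RP2D, a primary endpoint under Section 2.4. If a site or the Safety Review Committee (SRC) took replacement to mean removal, a DLT would leave the count and a new patient would take the slot. That error favours escalation.

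**Working it through.** The plan states no operating characteristics for its 3+3 design, so there is no figure of its own to reproduce.

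**Inputs**

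- MS-553 is taken twice daily. The DLT period is 28 days in A1 (Section 3.3.1) and Cycle 1 in B1 (Table 4), so 28 × 2 = 56 doses. In C1 it is Cycles 1 to 4 (Table 5), so 112 × 2 = 224 doses.
- The thresholds are at least 75% received (Section 3.3.2) and more than 25% withheld (Section 3.3.5).
- An interruption longer than 28 days forces discontinuation (Section 6.1.7).
- The true DLT rate p is not in the documents. I assume 0.25, 0.33 and 0.40.

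**Step 1: who is caught**

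- A1 and B1: 25% of 56 is 14, so the withheld-dose DLT needs at least 15 missed doses. At most 41/56 = 73.2% is received, which is below 75%. Fifteen doses is a 7.5-day hold, well inside the 28-day limit, so resumption is realistic. A 7-day hold misses 14 doses and leaves 42/56 = 75.0%, so that patient stays evaluable. Patients with other kinds of DLT are caught only if they too miss 15 or more doses.
- C1: 25% of 224 is 56, so at least 57 doses must be missed and at most 167/224 = 74.6% is received. One 28-day hold misses 56 doses and leaves 168/224 = 75.0%. A longer single hold forces discontinuation, which meets the second criterion. In C1 the gap therefore arises mainly from several shorter holds.
- A1 Dose Level 0: the gap is largely closed. The synopsis (Statistical methods) has patients with unacceptable Cycle 1 toxicity at that level stop MS-553, and Section 6.1.7 allows no single-agent reduction below 100 mg BID.

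**Step 2: one patient followed through the rules (A1 or B1, 15 doses withheld, then resumed)**

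| Rule | Result |
|---|---|
| DLT definition (3.3.5) | Has a DLT |
| Evaluability criterion 1 (3.3.2) | Not met: 73.2% |
| Evaluability criterion 2 (3.3.2) | Not met: treatment continues |
| Replacement (3.3.2) | Replaced |
| 3+3 count (3.3.2) | Has experienced a DLT; effect of replacement not stated |

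**Step 3: what the reading does to the decision**

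Suppose one of the first three patients has such a DLT, the other two have none, and the SRC makes no correction.

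- Counted in its slot: the cohort expands to 6 and passes only if three more patients are DLT-free, probability (1−p)³.
- Replaced and removed: it passes if the replacement is DLT-free, or if the replacement has a DLT and the three expansion patients do not, probability (1−p) + p(1−p)³.
- Counted, with a replacement also enrolled (my assumption: 6 evaluable patients plus this one, and no further DLT allowed): the next four must all be DLT-free, probability (1−p)⁴.

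| p | Counted in slot | Replaced and removed | Counted, replacement added |
|---|---|---|---|
| 0.25 | 0.422 | 0.855 | 0.316 |
| 0.33 | 0.301 | 0.769 | 0.202 |
| 0.40 | 0.216 | 0.686 | 0.130 |

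At p = 0.33: 0.67³ = 0.301; 0.67 + 0.33 × 0.301 = 0.769; 0.67⁴ = 0.202. A simulation of 400,000 runs agrees for the first two readings (0.301 and 0.770).

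**The case against.** The strongest reply is that the counting rule carries no evaluability filter. It counts patients, not evaluable patients, and one DLT in three makes expansion to 6 mandatory. Replacement adds a patient; nothing subtracts an event. Section 7.1 limits DLT determination by period and cohort only. Section 3.5 gives the SRC data "for all patients dosed within a given cohort in order to make a decision regarding dose escalation to the next dose level", and escalation is decided by the Investigators, the SRC and the Sponsor, not by an automatic 3+3 output. All of this stands. It makes counting the better reading and limits the harm, and the 77% figure requires departing from that reading. It does not repair an evaluability rule that still calls the patient non-evaluable, and it does not settle the denominator.

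A second reply is that discontinuing may include a temporary stop. Section 6.1.12 describes a hold as a temporary discontinuation, and Section 5.2.4.4 allows rituximab to be discontinued temporarily or permanently. This is weak, because Section 6.1.7 and Appendix 2A treat holding or interrupting MS-553 as something different from discontinuing it.

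A third reply is that little escalation remains exposed. In A1 an initial RP2D has been identified, C1 is narrowly affected, and no document shows that such a patient was ever replaced. This is fair on scope. It leaves B1, and the question of how past A1 patients were counted. Safety summaries on the ITT population (Section 8.5.1) would still include anyone dosed.

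**Conclusion.** The concern holds: the evaluability rule is wrong as written. Followed literally, it has one of two effects: an unnecessary replacement, or the loss of a DLT from a count that feeds a primary endpoint, in the direction that favours escalation. In the conditional case above, at p = 0.33, the three readings give pass probabilities of 20%, 30% and 77%.

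These are worst-case figures. They rest on the assumed p, on a particular outcome in the first three patients, and on no SRC correction. A figure for a whole dose level would need the share of DLT patients who hold and resume, which the documents do not give, so I offer none. The point should be fixed, but it does not undermine the design.

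**What to change.** In Section 3.3.2 and in the synopsis text for A1, B1 and C1, make two short edits:

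1. Replace the second evaluability criterion with a statement that any patient who experiences a DLT in the DLT period is evaluable and counted, whether or not MS-553 is discontinued.
2. Limit replacement for receiving under 75% of doses to patients without a DLT.

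Then check any escalation patient already replaced for under-75% exposure against the Section 3.3.5 definition, and correct the count if a DLT was left out.

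The cost is two edits in each of four places and one look-back. No extra patients are needed, and no dose or treatment rule changes.
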